The medical monitor will review and assess the inquiry within one business day; however, a response to the site may be delayed beyond one day if additional information is required or if input is required from the sponsor.

Project Manager Initial Review

PM/CTM enters the inquiry description into ePIP on behalf of (OBO) the site, attaches the paper PIF, and completes the PM/CTM portion based on protocol criteria or client directive.
PM/CTM consults with the client as needed
PM/CTM determines if MM review is necessary

If MM review not necessary:

- PM/CTM sends completed PIF to the Investigator
- PM/CTM enters clinically reviewed PIFs into ePIP OBO the site and attaches a copy of the completed paper PIF and complete ePIP workflow.
- PM/CTM files the PIF in the appropriate section of the study file.

Protocol Inquiry by Phone or Email:

(Only to be used if ePIP or PIF is not an option.)
***Note: sites are encouraged to call the safety hotline to speak to the MM for urgent questions. Calls should be followed by an ePIP submission documenting the question and response for documentation purposes.**

An email or Phone Contact Report (PCR) MUST include the following:

- Client Name/Protocol ID
- Site ID: PI Name and Site #
- Subject ID: Subject # and Initials
- Summarized question being asked by the site or PM
- Summarized resolution of Inquiry

The PM/CTM and SA should be copied on the email.

The SA will submit the inquiry in ePIP OBO the site, attach a copy of the email or PCR, and send the original to the study file.

- Note: PCRs entered into ePIP must follow the ePIP workflow through the PM and MM for tracking purposes**

- SA sends the completed ePIP or paper PIF to the Investigator and PM
- SA enters medically reviewed paper PIFs into ePIP system On Behalf Of (OBO) the site and attaches a copy of the completed paper PIF.

- Note: Paper PIFs entered into ePIP after completion must follow the ePIP workflow through the PM and MM for tracking purposes

- An electronic copy of the PIF is maintained in ePIP.
- SA sends the paper PIF to the appropriate section of the study file.

- Clinical team checks ePIP for pending PIFs
- Clinical team assures follow up requests are complete at the site

Holidays, After-Hours and Absence of Primary Medical Monitor

10.5. Appendix 5: Liver safety: suggested actions and follow-up assessments

Phase 3 liver chemistry stopping and increased monitoring criteria have been designed to assure participant safety and evaluate liver event etiology.

Phase 3 liver chemistry stopping criteria and required follow-up assessments

Liver Chemistry Stopping Criteria	
ALT absolute	ALT $\geq 8 \times$ ULN
ALT increase	ALT $\geq 5 \times$ ULN but $< 8 \times$ ULN persists for ≥ 2 weeks ALT $\geq 3 \times$ ULN but $< 5 \times$ ULN persists for ≥ 4 weeks
Bilirubin^{a,b}	ALT $\geq 3 \times$ ULN and bilirubin $\geq 2 \times$ ULN ($> 35\%$ direct bilirubin)
INR^b	ALT $\geq 3 \times$ ULN and INR > 1.5
Cannot monitor	ALT $\geq 5 \times$ ULN but $< 8 \times$ ULN and cannot be monitored weekly for ≥ 2 weeks ALT $\geq 3 \times$ ULN but $< 5 \times$ ULN and cannot be monitored weekly for ≥ 4 weeks
Symptomatic^c	ALT $\geq 3 \times$ ULN associated with symptoms (new or worsening) believed to be related to liver injury or hypersensitivity
Required Actions and Follow-up Assessments	
Actions	

 Immediately discontinue study intervention Report the event to GSK/PPD within 24 hours Complete the liver event eCRF and complete an SAE data collection tool if the event also meets the criteria for an SAE^b Perform liver event follow-up assessments Monitor the participant until liver chemistries resolve, stabilize, or return to within baseline (see MONITORING below) Do not restart/rechallenge participant with study intervention If restart/rechallenge not allowed or not granted, permanently discontinue study intervention and continue participant in the study for any protocol-specified follow-up assessments 
MONITORING: For bilirubin or INR criteria:
 
 Repeat liver chemistries (include ALT, AST, alkaline phosphatase, bilirubin) and perform liver event follow-up assessments within 24 hours 	
 Viral hepatitis serology^d Only in those with underlying chronic hepatitis B at study entry (identified by positive hepatitis B surface antigen) and quantitative hepatitis B DNA Obtain INR and recheck with each liver chemistry assessment until the transaminase values show downward trend Obtain blood sample for PK analysis, within 24 hours after last dose^e Serum creatine phosphokinase and lactate dehydrogenase Fractionate bilirubin, if total bilirubin $\geq 2 \times$ ULN Obtain complete blood count with differential to assess eosinophilia Record the appearance or worsening of clinical symptoms of liver injury, or hypersensitivity, on the AE report form Record use of concomitant medications on the concomitant medications report form including acetaminophen, herbal

[figure not shown]

 Monitor participant twice weekly until liver chemistries resolve, stabilize, or return to within baseline A specialist or hepatology consultation is recommended 
For all other criteria:
 
 Repeat liver chemistries (include ALT, AST, alkaline phosphatase, bilirubin) and perform liver event follow-up assessments within 24 to 72 hours Monitor participants weekly until liver chemistries resolve, stabilize, or return to within baseline 	remedies, other over-the-counter medications 
 Record alcohol use on the liver event alcohol intake eCRF page 
For bilirubin or INR criteria:
 
 Antinuclear antibody, antismooth muscle antibody, type 1 antiliver kidney microsomal antibodies, and quantitative total immunoglobulin G (IgG) or gamma globulins Serum acetaminophen adduct HPLC assay (quantifies potential acetaminophen contribution to liver injury in participants with definite or likely acetaminophen use in the preceding week [James, 2009]). NOTE: not required in China Liver imaging (ultrasound, magnetic resonance, or computed tomography) and/or liver biopsy to evaluate liver disease; complete liver imaging and/or liver biopsy eCRFs
---	---

- a. Serum bilirubin fractionation is to be performed if testing is available. If serum bilirubin fractionation is not immediately available, discontinue study intervention for that participant if ALT $\geq 3 \times$ ULN **and** bilirubin $\geq 2 \times$ ULN. Additionally, if serum bilirubin fractionation testing is unavailable, **record presence of detectable urinary bilirubin on dipstick**, indicating direct bilirubin elevations and suggesting liver injury.
- b. All events of ALT $\geq 3 \times$ ULN **and** bilirubin $\geq 2 \times$ ULN ($>35\%$ direct bilirubin) or ALT $\geq 3 \times$ ULN **and** INR >1.5 , which may indicate severe liver injury (possible 'Hy's Law') **must be reported as an SAE (excluding studies of hepatic impairment or cirrhosis)**; the INR threshold value stated will not apply to participants receiving anticoagulants.
- c. New or worsening symptoms believed to be related to liver injury (such as fatigue, nausea, vomiting, right upper quadrant pain or tenderness, or jaundice) or believed to be related to hypersensitivity (such as fever, rash, or eosinophilia).
- d. Includes: hepatitis A IgM antibody; hepatitis B surface antigen and hepatitis B core antibody; hepatitis C RNA; cytomegalovirus IgM antibody; Epstein-Barr viral capsid antigen IgM antibody (or if unavailable, heterophile antibody or monospot testing); hepatitis E IgM antibody. In those with underlying chronic hepatitis B at study entry (identified by positive hepatitis B surface antigen) quantitative hepatitis B DNA and hepatitis delta antibody. If hepatitis delta antibody assay cannot be performed, it can be replaced with a PCR of hepatitis D RNA virus (where needed) [Le Gal, 2005].
- e. PK sample will only be collected for an overdose. Record the date/time of the PK blood sample draw and the date/time of the last dose of study intervention prior to PK blood sample draw on the eCRF. If the date or time of the last dose is unclear, provide the participant's best approximation. If the date/time of the last dose cannot be approximated OR a PK sample cannot be collected in the time period indicated above, do not obtain a PK sample. Instructions for sample handling and shipping are in the laboratory manual.

Phase 3 liver chemistry increased monitoring criteria with continued therapy

Liver Chemistry Increased Monitoring Criteria – Liver Monitoring Event	
Criteria	Actions

ALT $\geq 5 \times$ ULN and $< 8 \times$ ULN and bilirubin $< 2 \times$ ULN without symptoms believed to be related to liver injury or hypersensitivity, and who can be monitored weekly for 2 weeks.
 
OR
 
ALT $\geq 3 \times$ ULN and $< 5 \times$ ULN and bilirubin $< 2 \times$ ULN without symptoms believed to be related to liver injury or hypersensitivity, and who can be monitored weekly for 4 weeks.
	
 Notify the GSK/PPD medical monitor within 24 hours of learning of the abnormality to discuss participant safety. Participant can continue study intervention. Participant must return weekly for repeat liver chemistries (ALT, AST, alkaline phosphatase, bilirubin) until they resolve, stabilize, or return to within baseline. If at any time participant meets the liver chemistry stopping criteria, proceed as described above. If ALT decreases from ALT $\geq 5 \times$ ULN and $< 8 \times$ ULN to $\geq 3 \times$ ULN but $< 5 \times$ ULN, continue to monitor liver chemistries weekly. If, after 4 weeks of monitoring, ALT $< 3 \times$ ULN and bilirubin $< 2 \times$ ULN, monitor participants twice monthly until liver chemistries normalize or return to within baseline.

10.7. Appendix 7: Clinical laboratory tests

- The tests detailed in [Table 9](#) will be performed by the central laboratory.
- Local laboratory results are only required in the event that the central laboratory results are not available in time for a response evaluation. If a local sample is required, it is important that the sample for central analysis is obtained at the same time.
- Protocol-specific requirements for inclusion or exclusion of participants are detailed in [Section 5](#).
- Additional tests may be performed at any time during the study as determined necessary by the investigator or required by local regulations.
- Investigators must document their review of each laboratory safety report.

Pregnancy testing

- Refer to [Section 5.1](#) for screening pregnancy criteria.
- WOCBP will only be included after a confirmed menstrual period and a negative urine pregnancy test.
- Pregnancy testing will be performed at Visit 1 (Baseline) before study intervention administration. The urine pregnancy test at Baseline will determine study contraception and abstinence requirements as follows:
 - Pregnancy testing at Visit 1 (Baseline) will be performed using the urine test kit provided to the study site (FIRST RESPONSE Early Result Pregnancy Test with a high sensitivity of ≤ 6.3 mIU/mL). Participants with a negative urine pregnancy test result from this test kit may be included in the study with no pretreatment contraception or abstinence requirements. WOCBP are not required to be using contraception or to have practiced abstinence within 14 days prior to study entry if the high sensitivity urine pregnancy test results are negative at Visit 1 (Baseline).
 - **Note:** *ONLY* if the study-specific pregnancy kit provided to the study site is unavailable, a standard urine pregnancy test with a sensitivity of 25 mIU/mL may be used as an exception. A participant with a negative urine pregnancy test result from the standard test may be included in the study *only* if the participant has used a highly effective contraception method as described in [Section 10.3.2](#) or has practiced abstinence from penile/vaginal intercourse for at least 14 days before receiving study intervention.
- Before Dose 5, an additional pregnancy test using the urine test kit provided to the study site (FIRST RESPONSE Early Result Pregnancy Test with a sensitivity of ≤ 6.3 mIU/mL) is required to be performed for WOCBP who have not used a highly effective contraception method (in [Section 10.3.2](#)) or have not practiced abstinence from penile/vaginal intercourse for at least 14 days prior to the first dose of study intervention. The urine pregnancy kit will be provided to the participant to perform as an outpatient during the defined window. For any participant with a positive pregnancy test result, study intervention must be immediately discontinued.

- Pregnancy testing will be performed whenever a menstrual cycle is missed or when pregnancy is otherwise suspected.
- Additional serum or urine pregnancy tests may be performed, as determined necessary by the investigator or required by local regulation, to establish the absence of pregnancy at any time during the participant's participation in the study.

Table 9 Protocol-required clinical safety laboratory tests

Laboratory Tests	Parameters	
Hematology	
 • Platelet count • RBC count • Hemoglobin • Hematocrit • RBC indices: 
 ◦ MCV ◦ MCH 	
 • WBC Count With Differential: 
 ◦ Neutrophils ◦ Lymphocytes ◦ Monocytes ◦ Eosinophils ◦ Basophils
Clinical chemistry^a	
 • Blood urea nitrogen/Urea • Potassium • Creatinine • Sodium • Calcium • Glucose (nonfasting) • Chloride 	
 • AST/SGOT • ALT/SGPT • Alkaline phosphatase • Total bilirubin • Direct bilirubin • Total protein • Magnesium • Phosphorus
Routine urinalysis	
 • Specific gravity • pH, glucose, protein, blood, ketones, nitrite, leukocyte esterase by dipstick • Microscopic examination (if blood or protein is abnormal) 
 ◦ Epithelial cells ◦ RBC ◦ WBC ◦ Casts ◦ Crystals 	
Pregnancy testing	
 • Highly sensitive urine hCG pregnancy test (as needed for WOCBP)^b 	
Other screening tests	
 • Follicle-stimulating hormone and estradiol (as needed in WONCBP only) • Serum or urine alcohol and drug screen (to include at minimum: amphetamines, barbiturates, cocaine, opiates, cannabinoids, and benzodiazepines) 	

NOTES:

- Details of liver chemistry stopping criteria and required actions and follow-up are given in Section 7.1.1 and Appendix Section 10.4. All events of ALT $\geq 3 \times$ ULN and bilirubin $\geq 2 \times$ ULN ($> 35\%$ direct bilirubin) or ALT $\geq 3 \times$ ULN and INR > 1.5 (if INR measured), which may indicate severe liver injury (possible Hy's law), must be reported to sponsor in 24 hours (excluding studies of hepatic impairment or cirrhosis).
- Local urine testing will be standard for the protocol unless serum testing is required by local regulation or IRB.

10.8. Appendix 8: AEs and SAEs: Definitions and procedures for recording, evaluating, follow-up, and reporting

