- i. With the exception of the urine dipstick and baseline pregnancy testing, a central laboratory will be used. Any baseline results received while participants are On-treatment that are exclusionary will be assessed by the medical monitor. The medical monitor will contact the investigator and advise on appropriate action with the study intervention.
- j. Measure temperature, blood pressure, respiratory rate, and pulse rate. See Section 8.3.2 for additional details.
- k. For women of childbearing potential, a negative high sensitivity urine pregnancy test is sufficient for eligibility. A pregnancy test will be performed predose and just before taking the fifth dose. The pregnancy test before the fifth dose will be done at home using a test kit supplied at Baseline, with the result confirmed at Visit 4.
- l. VRCC will confirm the doses of study intervention taken the previous day and results of at home pregnancy tests. AEs will not directly be asked about by VRCC, and VRCC will direct any AEs, SAEs, or concomitant medications reported during telephone visits directly to the study site; the study physician or otherwise appropriate medically trained staff from the study site will follow-up with the participant.
- m. The study physician or otherwise appropriate medically trained staff from the study site will perform a safety telephone call at Visit 6 (CCI [REDACTED]), and at Visit 7 (± 3 days). The study physician or otherwise appropriate medically trained staff from the study site will follow-up with participants who report an AE, SAE, or use of a concomitant medication to VRCC.
- n. CCI
[REDACTED]
- o. Participants must have taken 2 doses of study intervention before the Visit 2 CSS telephone assessment. This will be confirmed during the Visit 2 telephone call. For any participants who have not received 2 doses of study intervention, a second telephone call will be scheduled to perform the CSS after the second dose has been taken.
- p. The CCI CCI will be administered to participants via a telephone interview performed by VRCC. These assessments will be performed by the same interviewer who determines the CSS. See Section 8.2.2 for additional information.

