5.1. Inclusion criteria

Participants are eligible to be included in the study only if all of the following criteria apply:

Age and weight

1. The participant is ≥ 12 years of age at the time of signing the ICF/IAF and has a body weight ≥ 40 kg.

Note: Although participants as young as 12 years of age may enroll in the study, study sites must follow their IRB guidelines. Enrollment will be contingent upon such approvals regarding the allowed lower age limit for clinical study participants.

Type of participant and disease characteristics

2. The participant has 2 or more of the following clinical symptoms of uUTI with onset <96 hours prior to study entry: dysuria, frequency, urgency, or lower abdominal pain based on investigator assessment (see Appendix Section 10.1).
3. The participant has nitrite or pyuria (presence of 3+/large leukocyte esterase) from a pretreatment clean-catch midstream urine sample per local laboratory procedures.

Sex

4. The participant is female.

Contraceptive use is to be consistent with local regulations regarding the methods of contraception for those participating in clinical studies.

- A female participant is eligible to participate if she is a WOCBP who is not pregnant as confirmed by a high sensitivity urine pregnancy test predose at baseline regardless of current or prior contraception use or abstinence, is not breastfeeding, or is not a WOCBP as defined in Appendix Section 10.3.1.2.

Note: Collection of pregnancy information, contraceptive guidance, and WOCBP definitions are provided in Appendix Section 10.3, and requirements for pregnancy testing during and after study intervention are located in Appendix Section 10.7.

- The investigator is responsible for review of medical history, menstrual history, and recent sexual activity to decrease the risk for inclusion of a woman with an early undetected pregnancy.

Informed consent

5. The participant is capable of giving documented informed consent/assent as described in Appendix Section 10.9.3, which includes compliance with the requirements and restrictions listed in the ICF/IAF and in this protocol.

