10.3. Appendix 3: Contraceptive and barrier guidance

10.3.1. Definitions

10.3.1.1. Woman of childbearing potential (WOCBP)

Women in the following categories are considered WOCBP (fertile):

- Adolescents of childbearing potential: Tanner stage ≥ 2 (post-thelarche) irrespective of the occurrence of menarche or following menarche.
- From the time of menarche until becoming postmenopausal unless permanently sterile (see below).

Note: Menarche is the first onset of menses in a young female. Menarche is normally preceded by several changes associated with puberty, including breast development and pubic hair growth.

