10.3.2. Contraception guidance

- Refer to Appendix Section 10.7 regarding pregnancy testing for female participants at Visit 1 (Baseline) and associated pretreatment contraception and abstinence requirements. Female participants who enter the study using contraception must continue to do so through 7 days after the last dose of study intervention.
- As described in Section 5.3, participants will be requested to abstain from sexual activity from Visit 1 (Baseline) through 7 days after the first dose of study intervention to prevent possible re-infection.

 • CONTRACEPTIVES^a ALLOWED DURING THE STUDY INCLUDE:

 • Highly Effective Methods^b That Have Low User Dependency Failure rate of <1% per year when used consistently and correctly

 • Implantable progestogen-only hormone contraception associated with inhibition of ovulation^c

 • Intrauterine device (IUD)

 • Intrauterine hormone-releasing system (IUS)^c

 • Bilateral tubal occlusion • Vasectomized partner 
 • Note: Vasectomized partner is a highly effective contraceptive method provided that the partner is the sole sexual partner of the WOCBP and the absence of sperm has been confirmed. If not, an additional highly effective method of contraception will be used. Spermatogenesis cycle is approximately 90 days. • Highly Effective Methods^b That Are User Dependent Failure rate of <1% per year when used consistently and correctly • Combined (estrogen- and progestogen-containing) hormonal contraception associated with inhibition of ovulation^c 
 • oral • intravaginal • transdermal • injectable • Progestogen-only hormone contraception associated with inhibition of ovulation^c 
 • oral • injectable • Sexual abstinence 
 • Note: Sexual abstinence is considered a highly effective method only if defined as refraining from heterosexual intercourse during the entire period of risk associated with the study intervention. The reliability of sexual abstinence needs to be evaluated in relation to the duration of the study and the preferred and usual lifestyle of the participant.

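### Appendix 10.7 adds a menstrual-period entry condition that Section 5.1 and the SoA contradict, and the dose-5 pregnancy test has two different scopes

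*Protocol*

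**What the plan says.** **Entry.** The pregnancy-testing part of Protocol Appendix 10.7 has this line: "WOCBP will only be included after a confirmed menstrual period and a negative urine pregnancy test". Two other places set the entry rule for WOCBP differently:

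- SoA footnote k (Section 1.3): "a negative high sensitivity urine pregnancy test is sufficient for eligibility".
- Inclusion criterion 4 (Section 5.1) requires that a WOCBP is not pregnant "as confirmed by a high sensitivity urine pregnancy test predose at baseline regardless of current or prior contraception use or abstinence", and is not breastfeeding. It names no menstrual period as a condition. The nearest text is a duty to review: "The investigator is responsible for review of medical history, menstrual history, and recent sexual activity".

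Section 10.3.1.1 counts adolescents at Tanner stage 2 or above as WOCBP "irrespective of the occurrence of menarche or following menarche".

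The cross-references point in different directions. Appendix 10.7 opens with "Protocol-specific requirements for inclusion or exclusion of participants are detailed in" Section 5, and then sends the reader to Section 5.1 for the screening pregnancy criteria. Section 5.1 says that "requirements for pregnancy testing during and after study intervention are located in Appendix Section 10.7". Section 10.3.2, however, refers sites to Appendix 10.7 "regarding pregnancy testing for female participants at Visit 1 (Baseline) and associated pretreatment contraception and abstinence requirements".

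**Dose 5.** Footnote k gives WOCBP a test before the first dose and another just before the fifth, done at home with a kit supplied at Baseline. It sets no contraception condition. A sentence of Section 8.3.5, and Appendix 10.7, require the additional test only for WOCBP who lack highly effective contraception or lack at least 14 days of abstinence before the first dose.

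**The concern.** These are operative rules on who may enrol and who must be tested, and they do not agree. Section 5 permits no waivers, so a site cannot settle the conflict case by case.

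On entry, a site that goes to Appendix 10.7, as Section 10.3.2 directs, and applies its line literally would turn away a premenarchal WOCBP who meets criterion 4. A site that enrols her under criterion 4 breaches the appendix line.

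At dose 5, whether some women take the only other scheduled pregnancy test depends on which page the site reads. Section 2.3.1 names pregnancy testing as a mitigation for fetal exposure and reports no data in pregnant women. A positive result requires immediate discontinuation. Four doses precede the test, so a positive result would spare up to 10 − 4 = 6 of the 10 doses.

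**Working it through.** The plan gives no figure to reproduce. The check sets the rules side by side.

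**Step 1: are the entry rules compatible?** Let P be a confirmed menstrual period and N a negative high-sensitivity urine test.

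- Appendix 10.7: inclusion only if P and a negative urine test both hold, so P is necessary.
- Footnote k: N is sufficient, so P is not necessary.
- Criterion 4: N and not breastfeeding, with no mention of P.

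A rule that makes P necessary and a rule that makes N sufficient conflict for anyone with N but not P.

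**Step 2: who has N but can never have P?** A participant at Tanner stage 2 or above before menarche is a WOCBP under Section 10.3.1.1. Criterion 1 admits her from age 12 and 40 kg, where the site's IRB allows that age. She can satisfy criterion 4 but not the appendix line. For women past menarche the conflict is less certain, because the appendix gives no method or recency for a confirmed period. If a site read it as a recent period, waiting for the next one is not an option in general: criterion 2 requires symptom onset less than 96 hours before entry.

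**Step 3: which entry rule governs?** Appendix 10.7 refers twice to Section 5 for entry criteria, and Section 5.1 refers to Appendix 10.7 for testing during and after study intervention. The sensible inference is that Section 5.1 governs and the menstrual clause is an error. It is an inference, because no general precedence rule is stated.

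**Step 4: who takes the dose-5 test under each reading?** The restricted wording joins two negatives (no contraception, no abstinence) with *or*. Literally, lacking either one triggers the test. The probable intent is that having either one exempts.

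| WOCBP group | Footnote k | Restricted, literal *or* | Restricted, either one exempts |
|---|---|---|---|
| Neither contraception nor abstinence | tested | tested | tested |
| Contraception only | tested | tested | exempt |
| Abstinence only | tested | tested | exempt |
| Both | tested | exempt | exempt |

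The readings differ only in the last three rows. The groups are not cleanly separate, because Section 10.3.2 lists abstinence through the whole period of risk as a highly effective method. The documents give no group sizes.

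**Step 5: which texts define the dose-5 scope?** Footnote k is the only clear all-WOCBP text. The Visit 2 reminder, the Visit 4 result check and footnote l mention the home test without saying who takes it. A later unqualified sentence in Section 8.3.5 follows the restricted one in the same bullet, so it may only give the timing of that additional test. The conflict does not depend on these: footnote k against Appendix 10.7 is enough.

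**The case against.** The strongest reply is that this hardly matters in practice. Appendix 10.7 defers to Section 5, so most sites will apply criterion 4. Because the menstrual line has no recency, the menstrual-history review already required by Section 5.1 can satisfy it for women past menarche. What remains is a small adolescent group, and the error would be over-exclusion, which exposes nobody to drug. All of this stands as to size. It does not remove the conflict, since Section 10.3.2 sends sites to the appendix for baseline testing.

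At dose 5, a reader might infer that women without contraception or abstinence could go untested. The documents do not support this: that group is tested under every reading in the table. Other safeguards also apply. Sexual abstinence is requested through 7 days after the first dose (Section 5.3), contraception in use at entry must continue through 7 days after the last dose (Section 10.3.2), and a test is done if a menstrual cycle is missed or pregnancy is suspected (Appendix 10.7). So the safety gain from one rule is small.

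It can also be said that choosing all WOCBP over the restricted rule is partly preference. That is fair. The reasons for it are that the SoA already states it and that it removes the ambiguous *or*.

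**Conclusion.** The protocol is wrong as written on both parts, and the point is minor.

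- **Entry:** the menstrual clause contradicts footnote k and criterion 4 and cannot be met by premenarchal WOCBP. Their number is not given. A reader might infer two entry rules of equal standing, or a threat to enrolment generally. The deferrals to Section 5 and the undefined recency of the period do not support that.
- **Dose 5:** the scope differs between footnote k and the restricted wording, and the restricted wording is itself ambiguous. Only women using contraception, abstinent, or both are affected.

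The conclusion on entry rests on the inference that Section 5.1 governs. The judgement that the safety gain is small rests on the lower pregnancy risk of the women affected. The primary estimand, the analyses and the planned numbers (about 90 enrolled, at least 82 evaluable) do not change.

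**What to change.** **Entry.** In Appendix 10.7, strike the menstrual-period half of the sentence, so that the negative urine test is the only condition left there. Keep the investigator's review of menstrual history in Section 5.1.

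**Dose 5.** Use the SoA rule throughout. In Section 8.3.5 and Appendix 10.7, replace the contraception and abstinence qualifier with all WOCBP. Footnote k then stands as written on this test.

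**Kit supply.** Appendix 10.7 names the study kit for the dose-5 test. Yet a woman may have been enrolled on the standard 25 mIU/mL test precisely because the site had no study kit. Add to Appendix 10.7 that the standard test may be used at dose 5 if the study kit is unavailable. Writing the standard-test exception into criterion 4 may also look attractive. Inserted directly, it would make entry depend on contraception or abstinence in a sentence that says these do not matter, so it is not part of this fix.

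**Cost.** Amendment text in Appendix 10.7 and Section 8.3.5, with the IRB and health authority approvals in Section 10.9.1. There is no new type of procedure, since the home test is already in the SoA. Against footnote k the change adds 0 tests. Against the restricted wording it adds some home kits. The ceiling is about 90, if every one of about 90 participants were a WOCBP and exempt; this is a bound and not an estimate.
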